### 7.1.1      **Laboratory Based Abnormalities**

All protocol-specified laboratory values will be reported as outlined in **Table 1** during the study, along with associated units and reference ranges. Results of unscheduled/SOC laboratory assessments should be reported as an unscheduled visit laboratory assessment only if associated with a TEAE. An investigator should assess the clinical significance for all abnormal laboratory values. In general, if either of the following conditions are met, the abnormal laboratory value may be clinically significant:

- The abnormality suggests a disease and/or organ toxicity that is new or has worsened from baseline.
- The abnormality is of a degree that requires additional active management, eg, change of dose, discontinuation of the drug, close observation, more frequent follow-up assessments, or further diagnostic investigation.

Therefore, a clinically significant lab value is generally one that indicates a new disease process, an exacerbation or worsening of an existing condition, or requires further action(s) to be taken.

A lab result should not be considered in isolation, but in the context of the patient's physical examination and available history (ideally including past and present medical problems, social history, family history, medications, and previous laboratory evaluations).

Isolated non-clinically significant (as assessed by the investigator) laboratory values should not be reported as adverse events.

Laboratory abnormalities considered clinically significant by the investigator should be reported as AEs (or SAEs, as applicable), although the diagnosis should always be reported as the AE if known (eg, treatment emergent fasting hemoglobin A1C values  $\geq 7.1\%$  on two consecutive laboratory evaluations would be reported as the AE of diabetes, with the abnormal A1C values supportive of this diagnosis).

### **7.1.2 Non-Treatment Emergent Adverse Events**

Any AE occurring after a patient provides informed consent that is related to the non-SOC screening procedures (eg, PV vaccination booster) and biopsy procedure will be assessed, recorded in the patient's source documents and the eCRF with attribution, regardless of causality or seriousness (non-TEAEs).

Any AE occurring from the time of informed consent to start of PVSRIPO infusion that are not considered related to a study required non-SOC screening procedure, should be reported as medical history. For example, if a patient had new onset seasonal allergies requiring medication after signing of ICF but before Screening Period 2, it would be reported as medical history.

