## 5.2.2 PVSRIPO Infusion (Day 0 or Day 1 [Visit 4])

Note: At the time of PVSRIPO infusion, emergency drugs, including epinephrine and diphenhydramine will be available and the neurologic status, oxygen saturation, and cardiac rhythm of the patient will be monitored. Drug infusion will occur in the neuro-intensive care unit (ICU) or neuro step down unit so that all other emergency facilities will be available.

- CBC with differential (Platelet count should be confirmed prior to PVSRIPO infusion as well as at time of catheter removal and should remain consistent with inclusion criteria 11. Should the platelet count be less than  $125 \times 10^9/L$  on the day of catheter removal, a platelet transfusion should be administered and platelet count confirmed to be greater than  $125 \times 10^9/L$  prior to catheter removal)
- PVSRIPO infusion should occur on the same day (Day 0) or the day after catheter placement (Day 1) to allow flexibility due to the longer infusion (6.5 hr) and complexity of scheduling the necessary components for the infusion (eg, operating room time, surgeon, support team, pharmacy time, radiology appointments). However, under extenuating circumstances (eg, unavoidable scheduling issues, delayed diagnosis from biopsy, issues with investigational product or other critical supplies), so long as the patient remains in the neuro-ICU or neuro step-down unit, the time from catheter placement to PVSRIPO infusion may be extended up to 72 h post-placement with Sponsor approval. This timeframe is in keeping with other agents delivered safely via CED via similar procedures for even longer periods of time, which was not associated with increased risk of infection [23, 24]. If infusion is delayed, it will be recorded in the eCRF and patient's source documents along with the rationale and the Sponsor's approval.
  - See **Section 6.2.4** for additional details pertaining to infusion of PVSRIPO

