### **7.1.3 Treatment Emergent Adverse Events**

Treatment emergent AEs will be noted from the time of PVSRIPO infusion through the time the patient comes off study/no longer meets the requirements for the per protocol population (as defined in **Section 8**) and 30 days thereafter. Any AEs related to the catheter placement without PVSRIPO infusion will be summarized separately (eg, patient withdraws due to AE experienced after catheter placement but before PVSRIPO infusion).

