## **7.2 Serious Adverse Events**

An SAE is any AE meeting the following criteria:

Death	An AE that results in death (note: death due to progression is not an AE/SAE but should be reported as noted in the eCRF completion guidelines).
-------	--

Life-threatening AE	An AE that places the participant, in the view of the Investigator, at immediate risk of death from the AE as it occurred (ie, does not include an AE that had it occurred in a more severe form, might have caused death).
Required or prolonged participant hospitalization	An AE that results in an initial participant hospitalization or prolongs an existing hospitalization of the participant. If a participant is hospitalized as part of the clinical use of the study treatment, the period of normal hospitalization will be based on the Investigator's judgement and experience. Hospitalizations longer than this period will be considered prolonged hospitalizations.
Persistent or significant disability/incapacity	An AE that results in a substantial disruption of a participant's ability to conduct normal life functions.
Congenital anomaly/birth defect	A congenital anomaly/birth defect that occurs in the offspring of a participant exposed to the study drug.
Important medical event	An AE that may not result in death, be life-threatening, or require hospitalization may be considered an SAE when, based upon appropriate medical judgment, the event may jeopardize the participant and may require medical or surgical intervention to prevent 1 of the outcomes listed above. Examples of such "important medical events" include allergic bronchospasm requiring intensive treatment in an emergency room or at home, blood dyscrasias or convulsions that do not result in participant hospitalization, or the development of drug dependency or drug abuse

SAEs must be reported by the Investigator to the Sponsor or designee within 24 h of discovery for all patients from the time of consent, while on study and for 30 days after 1) completion of study participation or 2) if patient is rendered off-study and in the follow-up period only. SAEs will be reported in the eCRF with instruction provided in the eCRF Completion Guidelines.

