#### **8.4.5 Safety Analysis**

The full safety analysis set will include all patients who were administered at least one dose of the PVSRIPO. The safety of study-required pre-infusion procedures including catheter placement, will also be summarized.

Separate summaries will be prepared for the primary safety analysis set, which is patients who received PVSRIPO and  $\geq 1$  dose of pembrolizumab. Patients who received PVSRIPO alone will be summarized separately (secondary safety analysis).

Summaries of TEAE will begin at the time of PVSRIPO infusion. Adverse events considered related to screening or other pre-infusion procedures that are not SOC (eg, PV booster, biopsy prior to infusion, catheter placement without PVSRIPO infusion) will be summarized separately (screening data set).

All safety endpoints for patients receiving PVSRIPO and  $\geq 1$  dose of pembrolizumab may be summarized overall and by the number of pembrolizumab treatments received while on study (eg, 1, 2 to 3, 4 to 6, etc.).

Adverse events will be summarized by highest grade per patient and by attribution according to CTCAE v5.0, using the latest version of MedDRA preferred term as event category and MedDRA primary system organ class body term as Body System category. Unless otherwise stated, adverse events will be displayed in terms of frequency tables by treatment group by decreasing frequency. Each patient will be counted only once within each preferred term or system organ class. If a patient experiences more than one AE (or laboratory value) within a preferred term or system organ class for the same recording period, only the AE with the strongest relationship or the worst severity, as appropriate, will be included in the summaries of relationship and severity.

Events meeting the criteria for a DLT or SAE, leading to discontinuation, resulting in death, etc., will be reported in additional summaries. Changes from baseline over time and abnormal laboratory values, vital signs and NANO and KPS will also be reported.

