#### Treatment-emergent Adverse Event (TEAE)

A TEAE will be an AE that occurred during the study on or after catheter placement. Additionally, it is assumed that an AE which was reported to have started on Day 1 without an associated onset time occurred on or after catheter placement.

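### Between catheter placement and infusion, the investigator's attribution decides whether a non-serious adverse event can reach the SAP's TEAE tables, because the SAP moved the TEAE start without changing the protocol's recording rule

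*Protocol*

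**What the plan says.** **SAP.** Section 3.2.6 sets the start of the treatment-emergent period: "A TEAE will be an AE that occurred during the study on or after catheter placement". No condition on attribution is attached. Section 4.2 defines the Safety Set as all enrolled participants with an infusion catheter placed. Section 5.8.1 keeps only events before catheter placement out of the AE tables, and it plans separate rows for events related to catheter placement.

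**Protocol, start of the TEAE period.** Section 7.1.3: "Treatment emergent AEs will be noted from the time of PVSRIPO infusion". Section 8.4.5 agrees: "Summaries of TEAE will begin at the time of PVSRIPO infusion".

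**Protocol, recording before infusion.** Section 7.1.2 has two parts. Events "related to the non-SOC screening procedures (eg, PV vaccination booster) and biopsy procedure" are recorded in the eCRF with attribution and labelled non-TEAEs. The second part covers "Any AE occurring from the time of informed consent to start of PVSRIPO infusion" and says that those "that are not considered related to a study required non-SOC screening procedure, should be reported as medical history".

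**Protocol, other recording text.** Section 7.1 says that all AEs go on the AE case report form. Section 7.2 requires SAEs to be reported "for all patients from the time of consent", in the eCRF, with no attribution condition.

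**Length of the window.** Under Section 5.2.2, infusion takes place on the day of catheter placement or the next day; the interval "may be extended up to 72 h post-placement with Sponsor approval".

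**The concern.** The frequency and severity of TEAEs is a primary safety endpoint. A TEAE table is meant to be blind to cause: every event in the window counts, and relatedness is a separate row. Here the analysis window opens at catheter placement, but recording without regard to causality clearly begins only at infusion. In between, the investigator's judgment of relatedness decides whether a non-serious event is on file as an AE at all.

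The gap falls in the operative period. Section 6.2.2.1 of the protocol lists hemorrhage, infection and loss of neurologic function among the risks of biopsy and catheter implantation. In recurrent glioblastoma a new symptom at that time can reasonably be put down to the tumor or to the procedure, and that choice moves the event out of the tables or into them. The filter leaves out events judged unrelated, so the all-cause rows would be too low for their own window.

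**Working it through.** No formula applies and the plan states no figure on this point, so there is nothing to reproduce. The check follows an event with onset after catheter placement and before infusion through both documents.

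1. **Judged related to biopsy or a non-SOC screening procedure.** Protocol 7.1.2 records it as an AE and calls it a non-TEAE. The SAP finds it in the AE data, sees an onset after catheter placement, and counts it as a TEAE.

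2. **Non-serious, judged unrelated.** Under the second part of 7.1.2 it goes to medical history. It meets the SAP's TEAE definition but is not in the AE data from which the tables are built. It appears only in the medical history listing (16.2.4.2).

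3. **Serious, judged unrelated.** Section 7.1.2 sends it to medical history. Section 7.2 has it reported as an SAE in the eCRF, and 7.1 puts all AEs on the AE form. Either outcome can be reached by following the text.

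4. **Judged related to the catheter, in a participant later infused.** The first part of 7.1.2 names the booster and the biopsy, but not catheter placement. Sections 7.1.3, 8 and 8.4.5 speak of catheter-related events in connection with placement without infusion. Section 7.1, however, asks for attribution to catheter placement specifically, and 8.4.5 says that the safety of catheter placement will be summarized. The intent to record such events is clear; the wording of 7.1.2 is incomplete.

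Events 1 and 2 can be clinically identical and differ only in attribution. After infusion starts, both would be recorded as AEs.

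**Does the precedence clause settle it?** Protocol Section 8 says that the SAP governs where the two differ. That fixes which TEAE definition is used for analysis. It does not move into the AE data an event that a site filed as medical history by following 7.1.2.

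**Is the change disclosed?** SAP Section 6 lists the changes to the planned analyses. Neither the earlier TEAE start nor the wider Safety Set is among them.

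**Size.** The window is the same or next day as planned and 72 h at most. For a participant with a catheter who is never infused, 7.1.2 gives no end point. The documents give no AE rate for this interval, so the number of events affected cannot be derived.

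**The case against.** The best case for the plan is that little is lost. The window is short. SAEs have their own route into the eCRF from consent, and many important events in a patient who has just had surgery would plausibly qualify as serious. Section 7.1 and the continuous AE row in Table 1 point toward full recording. Sites also follow eCRF completion guidelines that are not part of these documents and may already resolve the matter. Most of this stands, and it limits the point in five ways.

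- A reader might infer that the serious-event rows are incomplete. The text does not show that. It shows two instructions that conflict for serious unrelated events.
- A post-catheter seizure blamed on the tumor looks like the natural example of a lost event. It is a poor one: Section 7.2 gives convulsions without hospitalization as an example of an important medical event, so many seizures would have the SAE route.
- A reader might say that these events vanish. They leave the AE tables but remain in the medical history listing.
- A reader might infer that new deficits are disguised as pre-existing. The SAP baseline is the last value before the calendar day of infusion, and Table 1 schedules no KPS or NANO on the catheter day, so the scheduled baseline normally comes from Screening Period 2. Both scales are then assessed daily until discharge and KPS change is summarized. Such a deficit can still show as a change, and worsening after infusion remains an AE.
- Never-infused participants might seem to have a long unrecorded period. Where the biopsy does not confirm tumor, Section 5.2.1 has the catheter removed and the patient withdrawn as a screen failure, so the period is brief.

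What the objection does not answer is the non-serious, unrelated event. Section 7.1.2 is the specific rule for this interval and overlaps the SAP's TEAE window, and nothing in the SAP brings such an event back.

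**Conclusion.** The mismatch is in the current text of both documents. Non-serious events judged unrelated, with onset between catheter placement and infusion, are left out of the SAP's TEAE tables by attribution. For serious events, 7.1.2 conflicts with 7.2 and with the general rule in 7.1, and these passages must be reconciled.

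The effect cannot be sized from the documents and is probably small, given a window of usually a day or less and a loss that is clear only for non-serious unrelated events. It is tempting to say that each lost event is worth 1/30 = 3.3 percentage points. That is not supported: the Safety Set is everyone with a catheter placed, not the 30 planned for the combination, and SAP Section 6 says that the full sample was not enrolled. The denominator could be smaller or larger.

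The conclusion assumes that sites followed 7.1.2 as written and that the eCRF guidelines do not override it. For never-infused participants it also assumes that they count as enrolled, and so belong to the Safety Set. This is a minor point on a primary safety endpoint, worth correcting because the correction is cheap.

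**What to change.** 1. **Recording rule.** In protocol 7.1.2 and the eCRF guidelines, record every AE regardless of causality from the start of biopsy/catheter placement. Name catheter placement beside biopsy. Keep the medical-history rule for earlier events only. This also removes the conflict with 7.1 and 7.2 for the window.
2. **Participants already treated.** A sentence added now does not recover events already filed. Before database lock, review medical-history entries with onset on or after catheter placement and move them to the AE data.
3. **One start point, disclosed.** Align protocol 7.1.3 and 8.4.5 with the SAP's start at catheter placement. List the earlier TEAE start and the wider Safety Set in SAP Section 6. Amending 7.1.2 alone would leave the two documents with different TEAE definitions.

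The cost is short text changes in the protocol, the eCRF guidelines and SAP Section 6, a few more AE entries, and one pre-lock data review.

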### **7.1.3 Treatment Emergent Adverse Events**

Treatment emergent AEs will be noted from the time of PVSRIPO infusion through the time the patient comes off study/no longer meets the requirements for the per protocol population (as defined in **Section 8**) and 30 days thereafter. Any AEs related to the catheter placement without PVSRIPO infusion will be summarized separately (eg, patient withdraws due to AE experienced after catheter placement but before PVSRIPO infusion).

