Secondary (efficacy)	
Anti-tumor activity:	
 
Disease Control Rate (DCR): Comprised of patients achieving CR, PR or SD for <math>\geq 6</math> months.
 
Duration of disease control (DDC): KM curves showing median DDC for patients with confirmed CR, confirmed PR or SD for <math>\geq 6</math> months.
 

Survival	
 
Overall and landmark survival: Proportion of patients alive at <math>\geq 6</math>, <math>\geq 12</math> and at 24 months post-PVSRIPO infusion as calculated by Kaplan-Meier methods.
 

Progression free survival	
 
If calculable, progression free survival (PFS) will be estimated based on the time from PVSRIPO infusion to death or confirmed progression, based on the definition of progression noted in Table 3.
 

Secondary (safety)	
	
 
Frequency and severity TEAE via CTCAE for patients receiving PVSRIPO alone without pembrolizumab (any reason).
 

Exploratory	
Identification of biomarkers of anti-tumor response to PVSRIPO followed by pembrolizumab	Assessment of tumor tissue and blood samples for identification of genetic, cytologic, histologic and/or other markers that demonstrate pharmacodynamic activity of PVSRIPO or correlate with anti-tumor response.
Alternative assessment of radiographic response/progression/PFS	Radiographic outcomes will also be analyzed as described in Table 3 for endpoint determination. All responses must be confirmed via two consecutive MRI assessments at least 4 weeks apart. If on bevacizumab therapy when response first noted, response will be confirmed $\geq 8$ weeks.
Patient-reported outcomes	Assessment of patient-reported quality of life and activities of daily living capabilities.
Study Design	This Phase 2 single-arm trial in patients with rGBM will characterize the efficacy, safety and tolerability of PVSRIPO intratumoral infusion followed by intravenous (IV) pembrolizumab 2 to 4 weeks later, and every 3 weeks, thereafter.

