#### 6.2.2.1 Potential Risks with Use

Detailed risks associated with PVSRIPO administration and use are outlined in greater detail in the Investigator's Brochure (IB). Based on an expanded Phase 1 trial and an ongoing multicenter Phase 2 trial, PVSRIPO may result in neurologic changes/exacerbation of existing and new-onset neurologic signs and symptoms due to peritumoral inflammation/edema within 12 months of PVSRIPO infusion. These changes are best managed with low dose dexamethasone and/or bevacizumab as described in [Section 6.5.4](#).

Intracranial hemorrhage at infusion catheter removal has also been noted. This has been mitigated by inclusion criterion [Number 11](#), requiring platelet counts  $\geq 125,000/\mu\text{l}$  (supported via transfusion acceptable) at the time of catheter placement/biopsy.

It is unknown if PVSRIPO can cause fetal harm; as such, female study participants and female partners of male study participants who are of childbearing potential should be advised to utilize effective forms of contraception for at least 30 days prior to and after any PVSRIPO infusion and for up to 4 months after the last dose of study drug received. Effective forms of birth control include using at least 2 methods, one of which should be a barrier method. Examples include:

- Condom
- Oral, injected, or implanted hormonal contraception
- Placement of an intrauterine device or intrauterine system

- Occlusive cap (eg, diaphragm or cervical/vault caps) with spermicidal foam/gel/film/cream/suppository
- Vasectomy or surgical castration  $\geq$  6 months prior to biopsy

**Surgical Complications:** The stereotactic tumor biopsies and catheter implantation procedure carries a risk for cerebrospinal fluid leak, infection, hemorrhage, loss of neurologic function, non-neurologic complications, and death. These risks depend primarily on the preoperative condition of the patient, the size and location of the tumor and associated diseases. In addition, as is standard with surgical procedures, potential complications for stopping anti-coagulation therapy prior to surgery may include heart attack, stroke, or other life-threatening blood clots. The potential risk for the patient will be discussed in detail with the patient and family by the treating neurosurgeon or the neurosurgeon's designee.

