### **7.5.3 Adverse Events of Immunologic Etiology Associated with Pembrolizumab**

Adverse events of an immunologic etiology have been associated with pembrolizumab exposure. These irAE may occur shortly after the first dose or several months after the last dose of pembrolizumab treatment and may affect more than one body system simultaneously. Therefore, early recognition and initiation of treatment is critical to reduce complications. Existing clinical trial data have shown that most irAEs related to pembrolizumab were reversible and could be managed with interruptions of pembrolizumab, administration of corticosteroids, and/or other supportive care. See **Section 6.5.4.3** on medication use for treatment of irAE.

Depending on the severity of the irAE, pembrolizumab will be temporarily withheld or permanently discontinued. In general, for an irAE requiring dose interruptions, low-dose dexamethasone ( $\leq 4\text{mg/day}$ ) should be initiated and tapered when the irAE is  $\leq$  Grade 1.

For a life-threatening irAE, IV dexamethasone should be initiated first followed by oral steroids. Other immunosuppressive treatment should also be initiated if the irAEs cannot be controlled by corticosteroids alone.

The next doses(s) of pembrolizumab will be withheld until the irAE has been reduced to  $\leq$  Grade 1 and dexamethasone dose has been tapered to  $\leq$  4mg/day and/or discontinued.

Pembrolizumab should be permanently discontinued if the irAE does not resolve within 12 weeks of last dose or dexamethasone cannot be reduced to  $\leq$  4 mg/day within 12 weeks.

- With regard to events  $\geq$  Grade 2 related to PTE or CE (eg, hemiparesis, seizure), pembrolizumab treatment should be held until those events resolve to  $\leq$  Grade 1. Pembrolizumab should be permanently discontinued for Grade 4 PTE or CE and/or events  $\geq$  Grade 3 related to PTE or CE.

**Refer to the most recent Keytruda® (pembrolizumab) package insert and “Guide for Keytruda®” for a list of adverse reactions for which pembrolizumab should be interrupted or permanently discontinued along with recommended management. This may include but not be limited to the following:**

- Immune-mediated pneumonitis: Withhold for moderate, and permanently discontinue for severe, life-threatening or recurrent moderate pneumonitis.
- Immune-mediated colitis: Withhold for moderate or severe, and permanently discontinue for life-threatening colitis.

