#### **8.4.6 Efficacy Analysis**

The full efficacy analysis set will include all patients who were administered at least one dose of PVSRIPO but patients receiving PVSRIPO alone will be analyzed separately from those who received PVSRIPO and  $\geq 1$  dose of pembrolizumab, which will be considered the primary efficacy analysis set.

All efficacy endpoints for patients receiving PVSRIPO and  $\geq 1$  dose of pembrolizumab will be summarized overall and in subgroups by the number of pembrolizumab treatments received while on study (eg, 1, 2 to 3, 4 to 6, etc.), for those with pembrolizumab interruptions, with treatment-related irAE, etc.

In addition, a per-protocol analysis will also occur to explore the impact of excluding patients from radiographic and survival primary analyses who:

- Underwent surgical resection of target lesions for control of PTE or CE or other reasons following-PVSRIPO infusion
- Received  $> 4$  mg/day dexamethasone or equivalent prior to or for  $> 14$  days after the first pembrolizumab treatment
- Received  $\geq 3$  consecutive treatments with bevacizumab at doses exceeding 7.5 mg/kg
- Received other non-protocol specified anti-tumor treatments
- Did not receive  $\geq 1$  dose of pembrolizumab (these patients will be replaced)
- Had major deviations, classified as follows:
  - Did not fulfill eligibility criteria
  - Met criteria for withholding or discontinuation of study treatments but continued treatment
  - Received incorrect study drug or dose of study drug.
  - Timing of study drug administration outside of protocol-specified windows
  - Received prohibited concomitant medication
  - Protocol-required procedure not adhered to
  - Other

The per-protocol analysis set will be identified prior to database lock.

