### **6. CHANGES IN THE PLANNED ANALYSES**

1. Day 0 is the earliest day that study drug is initiated but will be designated as Day 1 based on implementation standards for the analysis.
2. Central imaging review was not completed; therefore, results from this will not be presented.
3. The following analyses will not be completed:
  - a. Durable radiographic response (DRR)
  - b. Duration of disease control (DDC)
  - c. Progression-free survival (PFS)
  - d. Analysis of Per-Protocol population
  - e. Analyses based on participant strata (prior anti-VEGF agents, prior chemotherapy use)
  - f. Analyses on the efficacy set and PP set for the following subgroups: baseline NANO score, KPS, prior bevacizumab and chemotherapy or other treatment use/failure, extent of surgery at diagnosis, MGMT promoter methylation status and/or other tumor genetic factors at diagnosis and baseline, lesion cross-sectional area at baseline, number of prior progressions, age, gender.

- g. Landmark survival at month 24
- h. Exploratory analyses including analysis of efficacy based on modified iRANO criteria in Section 8.4.6.1, Table 3 of the protocol, identification of biomarkers of anti-tumor response to lerapolturev following by pembrolizumab or assessment of patient reported outcomes
- 4. The entire anticipated sample size of patients was not enrolled.

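### Protocol 7.1.3 ends TEAE collection on loss of per-protocol status, which can itself follow from toxicity or from not receiving pembrolizumab, and other sections imply continued collection

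*Protocol*

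**What the plan says.** Protocol 7.1.3 collects TEAEs from infusion "through the time the patient comes off study/no longer meets the requirements for the per protocol population", with a pointer to Section 8, "and 30 days thereafter". Section 8.4.6 holds the only list of per-protocol exclusions. It includes patients who "Underwent surgical resection of target lesions for control of PTE or CE or other reasons following-PVSRIPO infusion", those who received more than 4 "mg/day dexamethasone or equivalent prior to or for" more than 14 days after the first pembrolizumab treatment, those given three or more consecutive bevacizumab treatments above 7.5 mg/kg, and those who had no pembrolizumab. The same section says the set will be fixed before database lock.

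TEAE frequency and severity is the primary safety endpoint in patients who received the combination, and a secondary safety endpoint in patients who received PVSRIPO alone.

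On duration of risk, Protocol 6.2.2.1 refers to "new-onset neurologic signs and symptoms due to peritumoral inflammation/edema within 12 months of PVSRIPO infusion". Section 7.5.3 says of immune-related events: "These irAE may occur shortly after the first dose or several months after the last dose of pembrolizumab treatment".

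The SAP defines a TEAE by its start only (3.2.6), runs by-visit safety summaries to Week 104 (5.8), and lists "Analysis of Per-Protocol population" among the analyses that will not be done (Section 6).

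**The concern.** A collection window should not close because of the outcome it is meant to measure. Two of the exits in 8.4.6, resection for edema and prolonged or early higher-dose dexamethasone, can be treatment for toxicity. A third, no pembrolizumab, defines the whole secondary safety population. If sites follow 7.1.3 literally, ascertainment ends early in patients selected by toxicity or by missing the second agent. They stay in the denominator of the crude percentages, so later events in them lower the reported frequencies by their absence. The Synopsis also foresees exploratory comparison of PVSRIPO-only with combination patients. Unequal windows would distort any adverse-event comparison of that kind.

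The rule is also hard to apply at a site, because it depends on a set that is finalised only before database lock and that the SAP no longer analyses.

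**Working it through.** The plan states no figure for this point, so there is none to reproduce. The check has three parts.

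**1. Length of the window under 7.1.3 as written.** Window = day of per-protocol exit + 30.

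Inputs:
- 30-day tail (7.1.3).
- PVSRIPO-only status settled by 4 weeks, Day 28 (3.2).
- Resection at about 4 weeks (6.2.2.1).
- First pembrolizumab on Day 14 to 28 (Table 1). Dexamethasone is assumed to run from that dose, so that more than 14 days is reached on the 15th day after it. A later start would move the exit later.
- Follow-up of at most 730 days (Table 1), and a 12-month edema period (6.2.2.1).

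| Route out of per-protocol | Exit day | Window ends | Share of 730 days | Share of 365 days |
|---|---|---|---|---|
| No pembrolizumab by Week 4 | 28 | 28 + 30 = 58 | 7.9% | 15.9% |
| Resection at about Week 4 | 28 | 28 + 30 = 58 | 7.9% | 15.9% |
| Dexamethasone, first dose Day 14 | 14 + 15 = 29 | 59 | 8.1% | 16.2% |
| Dexamethasone, first dose Day 28 | 28 + 15 = 43 | 73 | 10.0% | 20.0% |

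If a PVSRIPO-only patient is taken never to have met the requirements, the window is 30 days (4.1% of 730).

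Few patients will live 730 days. Protocol Section 1 gives a median survival of 6 to 10 months. With exponential survival (an assumption), λ = ln 2 / (median × 30.4375), and expected person-days to day t are (1 − e^(−λt))/λ:
- Median 6 months: 52.1 of 247.0 person-days fall within 58 days, or 21%.
- Median 10 months: 54.3 of 355.8, or 15%.

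**2. What an under-count could look like (illustration only).** Assume a constant event hazard and ignore death. A true 12-month risk of a new event of 20%, 40% or 60% would be seen as 3.5%, 7.8% or 13.5% by Day 58, from 1 − (1 − P)^(58/365). If 10% to 30% of a group left at Day 28, a true 40% would appear as:
- 0.9 × 40% + 0.1 × 7.8% = 36.8%, at 10% leaving.
- 0.7 × 40% + 0.3 × 7.8% = 30.3%, at 30% leaving.

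The hazard and the share leaving are not in the documents. If events cluster early, the loss is smaller.

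**3. The passages side by side.**
- Pointing to early closure: 7.1.3 with 8.4.6. Section 7.2 also ends SAE reporting 30 days after a patient is off study and in follow-up only. Section 5.5, whose title refers to off-study participants, covers patients who have lost per-protocol status. Read together, the same exit could start the SAE clock. The data items listed in 5.5 do not name adverse events, though the list is stated to be open.
- Pointing to continued collection: Table 1 shows adverse events as continuous. Section 4.5 keeps replaced patients in safety follow-up. Section 5.5 sends patients who lose per-protocol status back to the Table 1 assessments at standard-of-care frequency. The Synopsis follows patients who stop pembrolizumab until their events resolve.
- Pointing to a narrower trigger: 5.3.4 explains per-protocol exit as starting non-study tumor treatment, and it too cites Section 8.

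A site could defend either practice from the text.

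**The case against.** The strongest reply is that 7.1.3 is loose wording and that the rest of the protocol shows the intent. Section 4.5 is specific to PVSRIPO-only patients and keeps them in safety follow-up. The Synopsis and 5.3.1 keep them on scheduled visits about every 9 weeks after Week 11. The opening of Section 8 treats patients as on study until progression, a major deviation such as prohibited tumor treatment, or a decision to stop, which fits the narrower gloss in 5.3.4. The list in 8.4.6 was written for radiographic and survival analyses. The SAP, which prevails where the two documents differ, puts no per-protocol end on a TEAE.

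Much of this stands. A reader might infer that collection does stop at Day 58 and that the safety endpoints are therefore biased. The documents do not establish that, because several passages direct the opposite. Nor do they support a claim about severe edema in general: edema managed within the protocol's limits does not cause per-protocol exit.

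Several things remain captured:
- The event that triggers exit is recorded and, under 7.1, followed to an outcome.
- Deaths and events of major clinical concern that the investigator links to the study stay reportable at any time (7.2).
- DLT counts are unaffected, since assessment ends at most 21 + 3 = 24 days after first pembrolizumab and exit after that dose still leaves 30 days.

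Section 6.2.2.1 also says only that edema-related changes may occur within 12 months, not that they are expected throughout.

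The reply does not remove the defect. Section 7.1.3 is the specific TEAE rule, it cites Section 8 without the 5.3.4 gloss, and the SAP cannot recover events that a site did not record.

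**Conclusion.** As written, the end of the TEAE window depends on toxicity management or on not receiving pembrolizumab, and it contradicts the protocol's other text on safety follow-up. On the literal reading, new events go uncollected after about Day 58 in PVSRIPO-only patients and in patients resected at about Week 4, and after about Day 59 to 73 with prolonged higher-dose dexamethasone. For the 58-day window this is 15% to 21% of expected person-time under exponential survival with a median of 10 or 6 months.

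These figures describe a window, not a measured bias. The documents give no rate of per-protocol exit or of late events, so the effect on the primary and secondary safety endpoints cannot be computed. What can be said is that any loss would be of new events after day +30 in a selected group, and that sites may have applied different rules. That is enough to require a change, because safety is a primary endpoint and the correction is simple.

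**What to change.** - Remove the per-protocol reference from Protocol 7.1.3.
- Define one TEAE window for every infused patient, independent of per-protocol status. It could run through the end-of-study visit, consistent with Table 1. Alternatively, it could run to 30 days after the first non-protocol anticancer therapy, with SAEs and adverse events of special interest collected beyond that.
- Align 7.2 and 5.5 with that window, name adverse events in the 5.5 data list, and reconcile Table 1, the Synopsis text on stopping pembrolizumab, 4.5 and 5.3.4 with it.
- For data already collected, have the SAP state the window actually applied, and report AE follow-up time or exposure-adjusted incidence, separately for combination and PVSRIPO-only patients.

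The cost is a wording amendment, some additional adverse-event entry at visits already scheduled, and one follow-up-time summary in the safety tables.
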